9.7.3. Analysis of Secondary Endpoints

Differences in time-to-event endpoints by treatment will be summarized with Kaplan-Meier curves and 95% confidence bounds.

Proportions will be used to summarize changes in ordinal scale at specific time points.

Duration of event will be determined according to median days with quartiles.

Binary data summarized as a percent with 95% confidence intervals. Comparisons between arms presented as differences in proportions with 95% confidence intervals.

Categorical data may be summarized according to proportions by category and/or odds ratios with confidence intervals.

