 - Time-weighted average change from baseline in viral shedding as measured by RT-qPCR in NP or OP swab samples (Phase II, III);
 - Time to SARS-CoV-2 RNA negative in NP or OP swab samples as determined by RT-qPCR (Phase II, III).
- Pharmacokinetics (PK) of SCTA01:
 - Pharmacokinetic characteristics in severe COVID-19 patients (Phase II).
- Immunogenicity of SCTA01:

- Immunogenicity assessment include the number and percentage of subjects who develop detectable ADA (Phase II, III).

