Urinalysis		X		X		X		X		X	
Serum chemistry		X		X		X		X		X	
Coagulation test		X		X		X		X		X	
IL-6		X		X		X		X		X	
Ferritin		X		X		X		X		X	
Procalcitonin		X		X		X		X		X	
Thrombin time		X		X		X		X		X	
D-dimer		X		X		X		X		X	
Immunogenicity blood samples							X		X	X	

PK samples				X ^{1,2}	X ¹	X ^{1,2}			X ^{1,2}		1: Intensive sampling of Phase II part: Blood samples will be collected in the same 30 subjects as the Table 3. 2. Sparse sampling of Phase II part: Blood samples will be collected in the remaining subjects (excluding the 30 subjects with intensive PK sampling) of each group of Phase II part.
Blood for SARS-CoV-2 test	X		X		X	X		X	X		Only performed while patient is in hospital or attends an in-person visit.
NP or OP swab for SARS-CoV-2 test	X	X	X	X	X	X		X	X		Continue testing at the scheduled time-point while hospitalized or attends an in-person visit, until the NP or OP swab samples viral RNA test is negative. NP swab preferred. If NP swab can't be obtained, OP swab may be used.
Sequencing the gene encoding spike protein		Will be tested in subjects who do not achieve a reduction in viral shedding or persistence viral presence or have a rebound in viral shedding following suppression									Using reserved NP or OP swab samples. No additional sampling is required.
8-Point Ordinal Scale	Daily until discharge			X	X	X			X		Only performed while patient is in hospital or attends an in-person visit, otherwise performed by phone call to assess clinical status (ordinal scale). The date and cause of discharge or re-hospitalization after discharge should be recorded.

Concomitant medications		Daily until discharge	
SpO ₂		Daily until discharge	Report the best reading if multiple readings are obtained in a day. Also record oxygen supplementation: low flow oxygen, high flow oxygen, or other.
AEs		Daily until discharge and biweekly via phone call after discharge until 120 days.	
ADE		Monitor for new infections and adverse events until 120 days (if discharged, via biweekly telephone call, in-person or virtual visit).	

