7.3.1. Time to Clinical Improvement

The subject's clinical status will be evaluated using the 8-point ordinal scale every day until Day 29 while being hospitalized. However, if the subject is discharged from the hospital before Day 15, Day 22, or Day 29, he/she only needs to come back to the hospital on Day 15, Day 22, and/or Day 29 for evaluation along with completing other procedures. If the discharged subject is unable to return for visits on these days, the evaluation can be done over the [contact]-Point Ordinal Scale

The ordinal scale is the primary measure of clinical outcome. The scale used in this study is as follows (from worst to best):

- 8: Death;
- 7: Hospitalized, on invasive mechanical ventilation or ECMO;
- 6: Hospitalized, on non-invasive ventilation or high flow oxygen devices;
- 5: Hospitalized, requiring supplemental oxygen;
- 4: Hospitalized, not requiring supplemental oxygen - requiring ongoing medical care (COVID-19 related or otherwise);
- 3: Hospitalized, not requiring supplemental oxygen - no longer requires ongoing medical care;
 - This would include those kept in hospital for quarantine/infection control, awaiting bed in rehabilitation facility or homecare, etc.;
- 2: Not hospitalized, limitation on activities and/or requiring home oxygen;
- 1: Not hospitalized, no limitations on activities.

To determine a subject's clinical status using the ordinal scale, the investigator should:

On Day 1, report their clinical status at randomization; On Day 2, report the clinical status from randomization to midnight on Day 1; On Day 3 through Day14 or until discharged and On Days 15, 22 and 29, provide the worst clinical assessment for the previous day [i.e., midnight to midnight; 00:00 ~ 23:59 (24-hr clock)]. For example, on Day 3 when completing the form, the worse clinical outcome measure of Day 2 is captured with the worst being death followed by ECMO, mechanical ventilation, etc. The Day 2 measurement is assessed as occurring anytime in that 24-hour period (00:00 ~ 23:59).

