7.4.1. Viral Load Assessment in NP or OP Swab Samples

As outlined on the Tables 3 and 4, NP or OP swab samples will be collected on Day 1; and Days 3, 5, 8, and 11 (while hospitalized); and on Days 15, 29, 120 (if attends an in-person visit or still hospitalized) or at early withdraw. Up to 29 days after administration, subjects who are virus positive should continue to undergo regular viral testing by NP or OP swab samples until the viral RNA test is negative.

NP samples should be taken from the same nostril for all tests.

If NP swab samples are not obtainable, oropharyngeal (OP) swab samples may be substituted, but make sure the position of swabs are consistent for the same subject.

Quantitative PCR for NP or OP swab samples will be done at central lab.

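### Time to RNA-negative is summarised by Kaplan-Meier although the Day 3 to 11 swabs depend on still being in hospital, so an arm discharged sooner has its viral clearance recorded later

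*Combined protocol and SAP*

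**What the plan says.** Section 1.5 lists "Time to SARS-CoV-2 RNA negative in NP or OP swab samples as determined by RT-qPCR" as a secondary endpoint for both phases. Section 9.7.3 gives one sentence for all secondary time-to-event endpoints: "Differences in time-to-event endpoints by treatment will be summarized with Kaplan-Meier curves and 95% confidence bounds". It names no test, no event date and no method for events known only to lie between two visits. Section 9.9 leaves the censoring rules for each such endpoint to be detailed later.

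The sampling is set out in three places.

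- Section 7.4.1: "NP or OP swab samples will be collected on Day 1; and Days 3, 5, 8, and 11 (while hospitalized"), then "and on Days 15, 29, 120 (if attends an in-person visit or still hospitalized"). Its next sentence asks that virus-positive subjects go on being swabbed regularly until negative, up to 29 days after dosing, and does not limit this to inpatients.
- Table 4 in section 7.1: "Continue testing at the scheduled time-point while hospitalized or attends an in-person visit".
- Section 7.3.1, on patients discharged early: "he/she only needs to come back to the hospital on Day 15, Day 22, and/or Day 29 for evaluation".

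**The concern.** A patient who clears virus on Day 6 and is still in hospital is found negative on Day 8. The same patient, discharged on Day 5 while positive, has no required swab until Day 15, so the first date on which clearance can be recorded is Day 15. The gap between swabs is about 3 days in hospital and about 10 days after an early discharge.

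Discharge is something the trial hopes to bring forward: it is a secondary endpoint, and scores 1 and 2 of the primary endpoint mean that the patient is out of hospital. The recording delay is therefore longer in the arm with the better clinical course. A Kaplan-Meier curve on swab dates shows that delay as slower clearance. At stake is the reading of one virologic endpoint: an arm could look slower to clear virus, or a real antiviral effect could look smaller, because its patients went home.

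**Working it through.** **Inputs from the plan.** There is no planning figure for time to RNA-negative. I borrow 95 + 255 = 350 patients per arm (section 9.3) and the TTCI assumption of section 9.4: exponential, placebo median 9 days, rate ratio 1.4. As a check, 9/1.4 = 6.43 days; the plan gives 6.5, which I use.

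**Assumptions of mine.** Discharge follows those TTCI figures. Clearance is exponential with the same median in both arms (5 to 12 days; 8 as the central case). Discharged patients attend Days 15 and 29. Clearance is independent of discharge in the central case.

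**Direct calculation, central case.** Counted from Day 1, the inpatient swabs fall at 2, 4, 7 and 10 days. With clearance median m and discharge median d,

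- share clearing between two swabs = 0.5^(s(j−1)/m) − 0.5^(s(j)/m)
- share still in hospital at swab j = 0.5^(s(j)/d)
- recorded negative by Day 11 = sum over j of the product of the two.

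| Study day | Clearing in interval (m = 8) | In hospital, placebo (d = 9) | In hospital, active (d = 6.5) | Product, placebo | Product, active |
|---|---|---|---|---|---|
| 3 | 0.1591 | 0.857 | 0.808 | 0.1364 | 0.1285 |
| 5 | 0.1338 | 0.735 | 0.653 | 0.0983 | 0.0873 |
| 8 | 0.1619 | 0.583 | 0.474 | 0.0944 | 0.0767 |
| 11 | 0.1248 | 0.463 | 0.344 | 0.0578 | 0.0430 |
| Sum | 0.580 | | | 0.387 | 0.336 |

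By Day 11 the true share cleared is 58% in both arms, but 39% (placebo) and 34% (active) are recorded. At Day 15 both catch up at 1 − 0.5^(14/8) = 70%.

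With m = 5 the same sum gives 0.2076 + 0.1349 + 0.1140 + 0.0597 = 0.516 for placebo and 0.1956 + 0.1198 + 0.0926 + 0.0444 = 0.452 for active. The recorded median is therefore Day 11 on placebo and Day 15 on active, with no true difference.

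**With a true antiviral effect.** Take a clearance hazard ratio of 1.4, so the active median is 8/1.4 = 5.71 days. The active arm's recorded share by Day 11 is 0.1847 + 0.1242 + 0.1095 + 0.0604 = 0.479 if discharge is equal, and 0.1740 + 0.1103 + 0.0890 + 0.0449 = 0.418 if it is discharged sooner. Against placebo at 0.387, the visible gap falls from 9.2 to 3.1 percentage points. The true gap is 70.3 − 58.0 = 12.3 points.

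**Simulation on first-negative-swab dates, no virologic effect, 350 per arm** (hazard ratio for clearance, active to placebo):

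| Setting | Hazard ratio |
|---|---|
| Central case | 0.94 |
| Clearance median 5 to 12 days, attendance 50 to 100%, clearance-discharge correlation 0 to 0.6 | 0.84 to 0.97 |
| Three days added to the hospital stay | 0.92 to 0.97 |
| Discharge rate ratio 1.2 instead of 1.4 | 0.94 to 0.97 |
| Equal discharge times | 0.99 |
| Every scheduled swab taken, in or out of hospital | 1.00 to 1.01 |

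The last two rows isolate the cause. Recorded dates fall on only a few days, so ties are heavy and the hazard ratio depends on the estimator. The values above behave like log-rank-score estimates; a Cox fit lies nearer 1 in the same direction. The recorded shares in the direct calculation do not depend on that choice.

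**Interval-censored fit on the planned swabs** (Weibull, full attendance, true median study day 9): placebo and active medians were 8.94 and 8.94 at correlation 0, 9.42 and 9.47 at 0.3, and 9.98 and 10.22 at 0.6. The gap between arms nearly disappears, with a small residual under strong correlation. This is a favourable case, since the Weibull family contains the exponential used to generate the data.

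**The case against.** **The plan names no test here.** True. Section 9.7.3 describes curves and bounds; the stratified log-rank test belongs to TTCI. A log-rank test on swab dates would call the active arm slower in about 4 to 38% of simulated trials at a nominal one-sided 2.5%. A reader might take that as an error rate of this trial. It is not; it only shows how strong the bias is. The curves are still the summary of differences between arms, and they carry the distortion.

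**Discharged patients may be swabbed.** The sentence in section 7.4.1 on continued testing covers exactly those who go home positive, and Table 4 allows a swab at any in-person visit. So it is too strong to say that such a patient can have no swab before Day 15. But neither text creates a visit before Day 15, and section 7.3.1 requires none. What stands is that these passages must be reconciled.

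**The rules are deferred.** Section 9.9 postpones censoring rules, but a censoring rule does not by itself settle how an event is dated. Censoring at the last inpatient swab gives 0.99 to 1.01 only if clearance and discharge are independent; it gives 0.93 to 0.96 at correlation 0.3, 0.83 to 0.89 at 0.6, and 1.04 at −0.3.

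**A working antibody would show through.** In one run with a true clearance hazard ratio of 1.4 and median 8 days, the swab-date estimate was 1.38 to 1.41 and no trial showed slower clearance. That looks unbiased, but the comparison should be with what the same estimator gives under equal discharge, about 1.45 to 1.50. In a run making that comparison, sooner discharge lowered it to 1.27 to 1.36 at medians of 5 and 8 days. The effect is weakened, not reversed. A reader might infer that clinical and virologic results will point in opposite directions; that would need a large clinical benefit with little or no antiviral effect, which the documents give no reason to expect.

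**Conclusion.** The concern holds in a limited form. The sampling rules and the choice of Kaplan-Meier are in the text; dating the event at the first negative swab is an inference, though swab dates are the only dates available. On that reading, an arm discharged sooner has its clearance recorded later. With no virologic effect the apparent hazard ratio is about 0.84 to 0.97 instead of 1.00, and a true effect is attenuated.

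The size rests on assumptions. TTCI stands in for discharge, although score 3 still means in hospital, and the documents state no discharge effect. Clearance medians, attendance and correlation are mine. With no difference in discharge between arms there is no bias.

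It would be wrong to infer that the trial's main conclusions are at risk. Success rests on TTCI, dose selection on Day 8 viral load, and no alpha or stopping rule uses time to RNA-negative. This is a change that should be made, not a flaw that undermines the design.

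**What to change.** 1. In section 9.7.3, define time to RNA-negative as interval-censored, from the last positive swab (open) to the first negative swab (closed), and right-censored at the last positive swab if no negative follows. Present Turnbull curves and an interval-censored proportional-hazards estimate. Keep Kaplan-Meier on swab dates as a secondary display, labelled as such.
2. State the event date and the handling of discharge for this endpoint among the rules that section 9.9 defers.
3. Reconcile the inpatient limit in section 7.4.1 with that section's sentence on continued testing, the in-person wording in Table 4 and the return visits in section 7.3.1, so that sites know whether a patient discharged while positive is swabbed before Day 15.

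Items 1 and 2 need wording and standard software, and no new data. The cost is slightly wider intervals. A small residual bias remains if discharge and clearance are strongly correlated.

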1.5. Secondary Endpoints

- Clinical efficacy of SCTA01:
 - Proportion of patients with initial clinical improvement at Day 29 (Phase II, III);
 - Proportion of patients with sustained clinical improvement at Day 29 (Phase II, III);
 - Time to initial clinical improvement up to Day 29 (Phase II, III);
 - Time to discharge from hospital, followed by being alive and home for 14 consecutive days prior to Day 90 (Phase II, III);
 - Proportion of patients discharged from hospital, followed by being alive and home for 14 consecutive days prior to Day 90 (Phase II, III);
 - All-cause mortality up to Day 29, record date and cause of death (if applicable) (Phase II, III);

- Percentage of subjects in each category on the 8-point ordinal scale (time frame: Days 3, 5, 8, 11, 15, 22, and 29) (Phase II, III);
 - Proportion of patients alive and free of respiratory failure up to Day 29 (Phase II, III);
 - Proportion of patients who are discharged from acute care up to Day 29 (Phase II, III);
 - Days of supplemental oxygen (if applicable) up to Day 29 (Phase II, III);
 - Days of non-invasive ventilation/high flow oxygen (if applicable) up to Day 29 (Phase II, III);
 - Days of invasive mechanical ventilation/extracorporeal membrane oxygenation (ECMO) (if applicable) up to Day 29 (Phase II, III);
 - Time to hospital discharge up to Day 29 (Phase II, III);
 - Number and proportion of non-responders having mutations in the gene encoding the SARS-CoV-2 S protein through Day 29. A non-responder is defined as a patient who does not achieve a reduction in viral shedding or persistence viral presence or have a rebound in viral shedding following suppression (Phase II, III).
- Safety of SCTA01:
 - Cumulative incidence of serious adverse events (SAEs) (Phase II, III);
 - Cumulative incidence of Grade 1, 2, 3 and 4 clinical and/or laboratory adverse events (AEs) (Phase II, III);
 - Discontinuation or temporary suspension of infusions (for any reason) (Phase II, III);
 - Chemistries, hematology, urinalysis, coagulation function, IL-6, ferritin, procalcitonin, thrombin time, D-dimer (Phase II, III);
 - Number and proportion of patients who are suspected to experience antibody-dependent enhancement (ADE) (Phase II, III).
- Virologic efficacy of SCTA01:
 - Change from baseline in viral shedding as measured by quantitative reverse transcription polymerase chain reaction (RT-qPCR) in NP or OP swab samples (Phase II, III);

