9.7. Efficacy Analysis

9.7.1. Primary Efficacy Analysis

The primary endpoint is TTCI up to Day 29. TTCI is defined as the time (in days) from randomization to the first day on which a patient satisfies point 1, 2, or 3 on the 8-point ordinal scale and maintains a score ≤ 3 at least 48 hours (initial improvement) and maintains this up to Day 29 (sustained improvement).

All deaths within 29 days or terminated early due to AE will be designated censored at Day 29 with respect to primary endpoint. Any subjects lost to follow-up or terminated early due to other reasons prior to an observed primary endpoint will be censored at the day of their last observed assessment. Subjects who completed follow-up but did not experience a primary endpoint event will be censored at the day of their Day 29 visit. The subjects who take prohibited medications will be regarded as treatment failures and will be censored at the time of medication use.

The primary analysis will use the stratified log rank test to compare treatment group to control group through Day 29 with respect to primary endpoint. Covariate factors may include country, duration of symptoms prior to enrollment, comorbidity and best supportive treatment. Note that if some strata are too small, they might be combined together to allow statistical method work well.

For each group, the Kaplan-Meier estimate of TTCI survival function will be constructed. Hazard ratio of SCTA01 vs. placebo with two-sided 95% CI will be derived from the stratified Cox proportional hazard model. The number of patients with a TTCI event and number of patients censored for the TTCI analysis will be summarized by treatment group.

The sensitivity analyses (such as using different population, different censoring rules and/or different covariates) for the primary endpoint will be fully described in the statistical analysis plan (SAP).

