9.9. Handling of Missing Data

For analysis of categorical secondary efficacy variables, missing data will be imputed using an NRI method (the participants with missing data will be considered non-responders). For time to event endpoints, different censoring rules will be detailed for each different endpoint respectively.

Details of the handling of dropouts or missing data will be fully described in the statistical analysis plan (SAP).

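### Days on oxygen and ventilation are summarised as raw medians with no rule for death, so early deaths can shorten the count and look favourable

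*Combined protocol and SAP*

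**What the plan says.** Section 1.5 (repeated in the synopsis) lists three secondary endpoints that count days on support: "Days of supplemental oxygen (if applicable) up to Day 29", the matching count for non-invasive ventilation or high-flow oxygen, and "Days of invasive mechanical ventilation/extracorporeal membrane oxygenation (ECMO) (if applicable) up to Day 29".

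Section 9.7.3 gives their whole analysis in one sentence: "Duration of event will be determined according to median days with quartiles". It names no test, no denominator and no treatment of death.

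Two other sections come close:

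- Section 9.7.1 has a death rule, limited to the primary endpoint: "All deaths within 29 days or terminated early due to AE will be designated censored at Day 29 with respect to primary endpoint".
- Section 9.9 begins: "For analysis of categorical secondary efficacy variables, missing data will be imputed using an NRI method". It then promises censoring rules for time-to-event endpoints and leaves dropouts and missing data to the SAP.

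**The concern.** A patient who dies on Day 5 while ventilated contributes at most 5 ventilator days. A survivor weaned on Day 15 contributes more. In a raw summary the death therefore looks like the better result. The 8-point scale in Section 7.3.1 orders them the other way, with death at 8 and invasive ventilation or ECMO at 7. Other secondary endpoints build survival in (alive and free of respiratory failure; discharged, then alive and at home), but these three do not.

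The qualifier *if applicable* raises a second question for two of the endpoints. Section 4.2 excludes patients on non-invasive ventilation or high-flow oxygen and those needing invasive ventilation, so any such use starts after entry. A median taken only over users would condition on an event that treatment may influence.

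At stake is how a descriptive table is read. If treatment changes mortality, the difference in raw medians can point the wrong way.

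**Working it through.** **1. Does any rule cover death for these counts?**

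| Rule | Applies to | Reaches the day counts? |
|---|---|---|
| Censoring at Day 29 (synopsis, Section 9.7.1) | primary endpoint | no |
| Non-responder imputation (Section 9.9) | categorical secondary variables | no, a day count is not categorical |
| Censoring rules to follow (Section 9.9) | time-to-event endpoints | no |
| Deferral to the SAP (Section 9.9) | dropouts and missing data | not clearly; a decedent's count is complete, not missing |

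The plan gives no figure to reproduce. What follows is illustration only, because the documents state neither mortality nor timing of death.

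**2. Ventilator days among ventilated patients.** Assumptions: durations follow a gamma distribution with shape 4, capped at 28 days; mortality m is 50% on control and 30% on active. With G the gamma distribution function, the raw median x solves

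m·G(x; mean of decedents) + (1 − m)·G(x; mean of survivors) = 0.5.

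| Mean, decedents | Mean, survivors | Raw median, control (m = 0.5) | Raw median, active (m = 0.3) |
|---|---|---|---|
| 4 | 14 | 6.4 | 9.5 |
| 6 | 14 | 8.2 | 10.1 |
| 8 | 14 | 9.6 | 10.9 |
| 10 | 14 | 10.8 | 11.6 |
| 12 | 14 | 11.9 | 12.3 |
| 14 | 14 | 12.9 | 12.9 |
| 14 | 10 | 10.8 | 10.1 |

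In the first five rows the arm with fewer deaths looks worse. The gap closes when durations are equal, and in the last row the raw medians point the correct way.

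If deaths are instead set to 28 days and survivors' mean is 14, the median solves (1 − m)·G(x; 14) = 0.5. This gives 17.0 at m = 30%, 20.4 at 40% and 23.9 at 45%. At 50% it reaches the ceiling of 28, so that last value says little in itself.

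**3. Oxygen days.** Assumptions: survivors' days are exponential with median 9, capped at 29. The 9 days is the placebo median time to clinical improvement in Section 9.4, borrowed as a proxy. Decedents stay on oxygen until death, and deaths are uniform over the stated window.

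| Mortality | Raw median, deaths Days 1–7 | Raw median, deaths Days 1–29 | Median with deaths set to 29 |
|---|---|---|---|
| 0% | 9.0 | 9.0 | 9.0 |
| 5% | 8.3 | 9.3 | 9.7 |
| 10% | 7.6 | 9.6 | 10.5 |
| 20% | 6.5 | 10.2 | 12.7 |
| 30% | 5.9 | 10.8 | 16.3 |

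With early deaths, higher mortality lowers the raw median. With deaths spread over the whole period it raises it a little. The favourable distortion is therefore specific to early death.

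**4. Would a median of free days work?** Suppose 10–20% of all patients are ventilated and the rest survive without ventilation, scoring 28 free days. Then at most 20% score below 28. That is less than 25%, so both quartiles and the median equal 28 in both arms. A median cannot show a difference here; a mean or a rank comparison can.

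**The case against.** The strongest defence is that these endpoints carry no inference. Section 9.7.3 attaches no test or alpha to them, and dose selection, futility and the efficacy boundaries do not use them. All-cause mortality, the proportion alive and free of respiratory failure, and the ordinal categories by visit are reported as well, so an imbalance in deaths would be visible. That stands and limits the weight of the point, but it does not correct the day counts themselves.

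Three stronger readings are tempting and are not supported:

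- *A drug that prevents deaths will look as if it prolongs support.* This needs decedents to have shorter support than survivors. It vanishes when durations are equal and reverses when decedents have longer support.
- *All three summaries are restricted to a subgroup formed after randomisation.* Not for oxygen: inclusion criterion 1 requires supplemental oxygen at entry. For the other two, restriction to users is one reading of *if applicable*, not a statement in the plan. Section 1.5 attaches the same words to the date and cause of death, where they only qualify what is recorded.
- *The plan chooses to score death as a good outcome.* It does not. That is a consequence of a missing rule, and the SAP text that might supply one is not in the supplied document.

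It can also be argued that stating the death rule and the denominator would be enough. That is the minimum. It would make the raw count transparent without giving a comparison that ranks death last.

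**Conclusion.** The gap is real. No rule covers death for the three day counts, and summarised as written they can place an early death ahead of a slow recovery. In the illustration for ventilated patients (50% against 30% mortality, survivors' mean 14 days) the misleading difference in medians is 9.5 − 6.4 = 3.1 days when decedents average 4 days, 10.1 − 8.2 = 1.9 at 6 days, 11.6 − 10.8 = 0.8 at 10 days, and nil at 14. Every one of these inputs is assumed.

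The open denominator concerns only non-invasive ventilation/high-flow oxygen and invasive ventilation/ECMO. A reader might infer that the trial's main conclusion is at risk. It is not: the primary test, alpha, sample size, dose selection and stopping boundaries do not depend on these endpoints. The change is worth making before unblinding, because a death rule chosen afterwards could alter the apparent direction of effect.

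**What to change.** In Section 9.7.3 and the SAP:

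- Add oxygen-free, non-invasive-ventilation/high-flow-free and ventilator/ECMO-free days to Day 29 in the ITT set. Score death by Day 29 as 0, and give survivors who never used the support the full number of free days.
- Report the distribution and mean by arm with a rank-based comparison labelled nominal. Do not rely on the median, which for ventilator-free days will probably sit at the maximum in both arms.
- Keep raw durations as description, shown separately for survivors and decedents, with the denominator (all patients or users) stated each time.

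The cost is SAP wording and one derived variable per endpoint. Date of death, and daily ordinal score and oxygen support until discharge, are already collected. Oxygen-free days also need a stated convention for home oxygen, because after discharge the ordinal scale is scheduled only at visits and category 2 combines home oxygen with limited activity. The downside is that a composite mixes mortality with duration and is harder to read than a plain day count; keeping the raw durations alongside offsets this.
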